2.2 General Methodology

All analyses will be performed separately for each of the treatment arms. Continuous measures will be summarized as n, mean, standard deviation, median, minimum and maximum. Categorical data will be summarized as frequency and percentage for each data category.

Where possible and indicated in Appendix 1 List of Tables , a pooled analysis will be performed with the OPTALYSE PE and OPTALYSE UK extension data combined. In each case, the same Analysis Subject Set for each population will be used.

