Enrollment:	
OPTALYSE PE 101 subjects were randomized and 100 treated in the OPTALYSE PE study and were followed for one year.
 
OPTALYSE PE – UK Extension (OPTALYSE UK) Up to 120 additional subjects were planned to be enrolled in the UK Extension study to obtain up to 75 efficacy evaluable subjects (25 efficacy evaluable subjects enrolled and randomized in each of 3 treatment arms.). Due to slow enrollment and the ability for sites to participate in the KNOCKOUT study, the OPTALYSE UK sites were instructed to stop enrollment on May 1, 2019. 29 subjects were enrolled in OPTALYSE UK and sites were instructed to continue following subjects for one 1 year per the protocol.
 
Evaluable subjects are those who have RV/LV assessments within specified windows and scores available at baseline and at 48 hours from the start of treatment.
																			

A. PROTOCOL SYNOPSIS

Clinical Sites:	
OPTALYSE PE 19 centers within the United States and the United Kingdom enrolled into OPTALYSE PE.
 
OPTALYSE PE – UK Extension (OPTALYSE UK) Up to 10 centers located in the United Kingdom were planned for OPTALYSE UK. At the time enrollment was stopped, 5 sites had enrolled subjects into OPTALYSE UK.

Time Course:	
OPTALYSE PE Enrollment into OPTALYSE PE took place from June 2015 through November 2016 with 1 year follow-up.
 
OPTALYSE PE – UK Extension (OPTALYSE UK) Enrollment into OPTALYSE UK took place from October 2017 through March 2019 with 1 year follow-up.

B. SCHEDULE OF ASSESSMENTS - OPTALYSE UK

	Screening/ Baseline ¹	Post APT Procedure				Follow-up - Clinic Visit			
	Day -2 within -48 Hrs. of APT start	Day 0 within 4 Hrs. of APT end	Day 1 24 Hrs. ±6 hrs of APT start	Day 2 48 Hrs. ±6 hrs of APT start	Day 3 72 Hrs. of APT start or D/C ¹⁰	Day 30 ± 5 D	Day 90 ± 10 D	Day 365 ± 14D	Early Term ¹¹
Informed Consent	X								
Demographics	X								
Medical History, Physical Exam, & Risk Factors	X								
Vital Signs ^{2,3}	X	X	X	X		X	X	X	X
Electrocardiogram	X								
CTA	X			X					
Hemodynamics/SvO ₂ ⁴	Optional								
PESI/sPESI	X	X	X	X					
Echocardiogram ^{5,6}	X	X	X	X		X	X	X	X
Laboratory Tests ⁷	X	X		X					
Biomarkers: Troponin, BNP/NT-proBNP, lactate/lactic acid, and D-dimer	X			X					
6 Minute Walk Test (6MW)						X	X	X	X
QOL Assessment: PEmb-QOL; EQ-5D- 5L						X	X	X	X
Adverse/VTE/Bleeding Events		X	X	X	X	X	X	X	X
Anticoagulant medications ⁸	X	X	X	X	X	X	X	X	X
Concomitant medications ⁹	X	X	X	X	X	X	X	X	X

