2.3 Efficacy Analyses

2.3.1 Primary Efficacy Analysis

The primary efficacy outcome is the change in the RV diameter-to-LV diameter ratio, from Screening/Baseline to 48 ± 6 hours after the start of the APT procedure, as determined by CTA. For each treatment arm, the mean RV/LV ratio change will be compared to the historical control value of a 0.20 reduction for the heparin arm¹. For this study, a 1-sided $p < 0.15$ by t test rejecting a ≤ 0.20 reduction will be regarded as a positive sign for further investigating a treatment regimen. As an example, should the standard deviation be 0.41 as observed in the SEATTLE II study, with 25 evaluable subjects the 1-sided p value would be <0.15 if the mean RV/LV ratio reduction is 0.29 or higher. To limit the 3-arm total false positive error rate to 0.15, the Hochberg procedure² will be used for statistical testing.

The main primary endpoint analyses will be performed for the ITT Subject Set and the Evaluable Subjects subset.

To explore a potential increasing trend in RV/LV ratio reduction for treatment Groups 1 through 3 as defined in Protocol Synopsis, i.e. Group 1 having the least reduction and Group 3 having the most reduction, an exploratory regression analysis will be performed on both absolute change and percent change data from all 3 groups. The independent variables will include baseline RV/LV ratio value, the unilateral vs. bilateral PE indicator, and treatment groups 1 through 3 coded ordinally as 1, 2, and 3. This exploratory analysis will only be performed on the ITT Subject Set.

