2.5 Sample Size And Power Estimation

The primary efficacy endpoint for the study is the 48-hour decrease in RV/LV ratio. The Fasullo¹ study's heparin arm indicated a mean RV/LV ratio decrease of 0.20. Based on these results, we propose a mean

48-hour RV/LV ratio (absolute) decrease ≤ 0.20 as the null hypothesis for this study. Rejecting the null hypothesis with a 1-sided $p<0.15$ by t test will be regarded as a positive sign for further investigating a treatment regimen. For submassive PE subjects in the SEATTLE II study, a mean RV/LV ratio reduction of 0.43 was observed with a standard deviation of 0.41. Should these results be true for a regimen in the current study, with 25 evaluable subjects, the power to detect a positive signal is approximately 0.96.

The simultaneous power for the three treatment groups at the planned sample size of with $n=25$ evaluable per arm is approximately 0.88 by the Hochberg procedure².

Appendix 1: List of Tables (All summaries and analyses will be by treatment arm for the UK Extension portion of the study unless otherwise specified. Except for RV/LV ratio analyses, all p values are 2-sided. Analyses that will be conducted for the combined portions of the study (OPTALYSE PE plus UK Extension) as well as for the UK Extension alone and are indicated by an asterisk.)

Subject Set = ITT for (1) – (20) Unless Otherwise Specified

- 1) Enrollment by Site
- 2) Demographics
 - a) Age
 - b) Weight
 - c) BMI
 - d) Gender
 - e) Ethnicity (Hispanic vs. not Hispanic)
 - f) Race
- 3) Clinical History and Risk Factors
 - (a) – (v) on *Clinical History and Risk Factors CRF*.
 - a) Hypercholesterolemia
 - b) Congestive Heart Failure
 - c) Hepatic Insufficiency
 - d) Renal Insufficiency
 - e) TIA or Stroke
 - f) Active Cancer
 - g) Diabetes
 - h) Hypertension
 - i) Tobacco use
 - j) $BMI \geq 30.0$
 - k) COPD
 - l) History of Cancer in Remission
 - m) Family History of VTE
 - n) Chronic Inflammatory Disorders
 - o) Acute Infectious Illness within 30 Days of signing ICF
 - p) Atherosclerotic Cardiovascular Disease
 - q) Currently taking a Hormonal Contraceptive or Replacement Therapy
 - r) Osteoarthritis of Either Hip or Knee

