11) Core Lab RV/LV ratio from CTA: Baseline, 48 hours Post APT Start, absolute difference (Post-Procedure - Baseline) and percent change*

Summarize as continuous data for all above, i.e. n, mean, SD, median, minimum, maximum; provide 95% CI's for mean absolute and percent changes; provide 1-sided and 2-sided p values testing reduction ≤ 0.20 by t test for mean absolute change from baseline; provide same p values testing reduction ≤ 0 by t test for mean percent change from baseline.

All analyses above for RV/LV ratio by CTA will be repeated for the efficacy evaluable patient subset for ITT patients.

Lastly, repeat the above analyses for ITT patients as 6 arms, i.e. unilateral vs. bilateral for each of the 3 randomization arms.

Using continuous data from all 3 arms, perform increasing benefit trend analysis as described in the last paragraph of Section 2.3.1 and provide the 2-sided p value. (ITT only)

12) Core lab echocardiogram: Baseline, within 4 hours of APT end, 24 and 48 hours post APT start, Day 30, Day 90, Day 365 (procedure start date = Day 0) and change from baseline at all post-baseline time points (for continuous endpoints a-c below, besides summarizing as n, mean, SD, median, minimum and maximum at each of the 7 time points, also provide box-wisker plots for all time points on the same graph)*

- RV/LV ratio (perform same analysis at all time points as for the primary endpoint of RV/LV ratio as described in (11) above with the exceptions that testing a mean reduction of 0.20 applies to the 48 hours time point only and binary endpoint applies to \leq baseline vs. $>$ baseline only) (ITT)
- TAPSE (perform same analysis at all time points as for the primary endpoint of RV/LV ratio as described in (11) above, except mean absolute changes from baseline are tested against 0 as opposed to 0.20 and all p values are 2-sided and binary endpoint applies to \leq baseline vs. $>$ baseline only) (ITT)
- Estimated RVSP (perform same analysis at all time points as for the primary endpoint of RV/LV ratio as described in (11) above, except mean absolute changes from baseline are tested against 0 as opposed to 0.20 and all p values are 2-sided and binary endpoint applies to \leq baseline vs. $>$ baseline only) (ITT)
- IVC collapse with respiration (summarize as frequency and proportion at each time point and 2 \times 2 tables for changes from baseline, provide p values by McNemar's test) (ITT)

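### The pooled between-arm models (trend regressions and 6-minute walk) have no term for study portion, although arms were randomised within each portion

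*SAP*

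**What the plan says.** SAP 2.2 (General Methodology) states that, where Appendix 1 marks it, "a pooled analysis will be performed with the OPTALYSE PE and OPTALYSE UK extension data combined". The opening note of Appendix 1 explains that starred analyses are "conducted for the combined portions of the study (OPTALYSE PE plus UK Extension) as well as for the UK Extension alone". Stars appear on item 11 (CTA RV/LV: "absolute difference (Post-Procedure - Baseline) and percent change"), item 12 (echocardiogram), item 15 (modified Miller score), the two quality-of-life instruments, item 17 (6-minute walk) and major bleeding.

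Three of these items contain a trend regression across arms. SAP 2.3.1 defines it: "The independent variables will include baseline RV/LV ratio value, the unilateral vs. bilateral PE indicator, and treatment groups 1 through 3 coded ordinally". The same section says "This exploratory analysis will only be performed on the ITT Subject Set", and item 11 asks the analyst to "perform increasing benefit trend analysis as described in the last paragraph of Section 2.3.1 and provide the 2-sided p value". SAP 2.3.2 repeats the model for RV/LV, TAPSE and RVSP by echocardiogram and for the Miller score. Item 17 asks for between-group comparisons of the 6-minute walk and names no model.

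No portion, site or period term is listed for any of these models, and the SAP describes no stratified pooling or heterogeneity check.

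The SAP synopsis shows how the portions differ. OPTALYSE PE randomised 101 subjects at 19 US and UK centres from June 2015 to November 2016. For the extension, "Enrollment into OPTALYSE UK took place from October 2017 through March 2019 with 1 year follow-up"; it enrolled 29 subjects at 5 UK sites.

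**The concern.** Randomisation balances the arms within each portion. A pooled comparison that ignores portion also uses differences between portions whenever the mix of the two varies by arm, and those differences are not randomised. Period, sites and local practice could all shift the mean RV/LV change or walk distance.

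Equal mixing cannot be taken for granted. The extension stopped at 29 of up to 120 planned subjects, and protocol 6.2 describes neither blocking nor stratification. The 6-minute walk is the most exposed item because it is first measured at Day 30, so no baseline value can absorb a cohort difference.

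At stake is the reading of the trend across Groups 1 to 3, which bears on the study's dose-and-duration objective, and the reader's ability to see whether the UK data agree with the first portion. Protocol 1.2 gives adding UK findings as one reason for the extension.

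**Working it through.** **1. The plan's own figures, to confirm the SD.** The SAP gives no figure for the pooled analyses. Its per-arm figures use SD 0.41, n = 25, null 0.20 and one-sided 0.15.
- Critical mean: 0.20 + 1.059 × 0.41/√25 = 0.287 (stated 0.29).
- Power at 0.43: noncentrality 0.23/0.082 = 2.80, giving 0.959 (SAP 0.96, protocol 0.95).
- All three arms: 0.959³ = 0.881 (stated 0.88).

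These agree, so SD 0.41 is used below.

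**2. Bias formula.** Let d be the cohort offset in RV/LV change and b the least-squares slope of the UK indicator on arm code (1, 2, 3). Leaving portion out biases the trend slope by d × b. The standard error is 0.41/√Sxx, where Sxx is the sum of squares of arm code about its mean. The model is simplified to arm, with or without portion.

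**3. One case by hand.** Assume first portion 34/33/33 and UK 14/9/6.
- Arm totals 48/42/39; mean arm code 249/129 = 1.930; Sxx = 86.4; SE = 0.41/√86.4 = 0.0441.
- Cross-product of UK indicator and arm code: 14(−0.930) + 9(0.070) + 6(1.070) = −5.98, so b = −5.98/86.4 = −0.069.
- With d = 0.20 the bias is −0.0138 per arm step, or 0.31 SE.

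**4. Range.** Splits and offsets are assumptions. The total is 129 or, if only 75 first-portion subjects fall in Groups 1 to 3, 104. Type I error is two-sided at an assumed 0.05, since the SAP states no level for the trend.

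| First portion + UK | d | Slope bias | SE without / with portion | Bias/SE (absolute) | Type I error |
|---|---|---|---|---|---|
| 34/33/33 + 10/10/9 | 0.20 | −0.0013 | 0.0442 / 0.0442 | 0.03 | 0.050 |
| 34/33/33 + 12/10/7 | 0.20 | −0.0085 | 0.0443 / 0.0444 | 0.19 | 0.054 |
| 34/33/33 + 14/9/6 | 0.10 | −0.0069 | 0.0441 / 0.0445 | 0.16 | 0.053 |
| 34/33/33 + 14/9/6 | 0.20 | −0.0138 | 0.0441 / 0.0445 | 0.31 | 0.061 |
| 25/25/50 + 10/10/9 | 0.20 | −0.0143 | 0.0433 / 0.0438 | 0.33 | 0.063 |
| 25/25/25 + 14/9/6 | 0.20 | −0.0166 | 0.0492 / 0.0498 | 0.34 | 0.063 |

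The sign follows the assumed direction of offset and imbalance. Adding portion removes the bias.

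**5. How likely is such a split?** Under simple randomisation of 29 subjects to three arms (an assumption), the SD of the difference between two arm counts is √(29 × 2/3) = 4.4. The 14 v 6 case is a difference of 8, about 1.8 SD: marked but possible.

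**6. Averaged over randomisations.** With 100 + 29 subjects, simple randomisation in each portion, 6,000 runs and offsets of 0.1 to 0.4, the mean slope is about zero. Type I error is 0.049 to 0.053 without the term and 0.050 to 0.054 with it.

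**7. 6-minute walk.** The documents give no SD. In the step 3 split the UK shares are 14/48 = 29.2% in Group 1 and 6/39 = 15.4% in Group 3, so an unadjusted Group 3 v 1 difference would carry 13.8% of any cohort offset in metres.

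**The case against.** The strongest reply is that nothing is shown to be wrong. Subjects are randomised among the arms, and protocol section 4 plans equal UK groups of about 30. Averaged over possible allocations, the trend test holds its level (step 6). The trend is labelled exploratory. Item headings specify core-laboratory readings for CTA, echocardiogram and Miller score, and the first portion also had UK centres, so the contrast between health systems is only partial. All of this stands, and it keeps the expected effect small. It does not remove the point: the analysis will be read given the split that actually occurred, which may be uneven with only 29 UK subjects, and portion is known for every subject.

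A reader might also infer that no cohort-specific results are planned. The opening note of Appendix 1 contradicts that, since every starred item is also run for the UK extension alone. What is not promised is the OPTALYSE PE estimate in the same table, or arm counts by portion.

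A reader might extend the criticism to the MMRM in SAP 2.3.2, which also lacks a portion term. But analyses are run separately by arm, that model lists no treatment term, and its output is an overall effect tested against zero. There is no arm contrast to confound.

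**Conclusion.** The omission is confirmed for the pooled trend regressions (CTA RV/LV, echocardiographic RV/LV, TAPSE and RVSP, Miller score) and for the pooled 6-minute walk comparison. The SAP's wording on what the regression will include might allow further covariates, but it names none.

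The tempting conclusion that cohort differences do distort the trend is not supported: it needs UK shares that differ by arm, and the documents give neither split. With equal shares the bias is zero. In the assumed imbalanced splits it is at most about 0.017 per arm step, or 0.34 SE. That rests on assumed offsets of up to 0.20, SD 0.41, a model without baseline and laterality, and 100 (or 75) rather than the 101 randomised first-portion subjects.

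Nor do the documents support a claim that the pooled tests against 0.20 are biased, or that a covariate would mend them. Those are one-sample t tests on arm means that mix the two cohorts by design. With 43 subjects per arm (assumed) and a UK share of 29/129 = 22%, an offset of 0.10 moves each pooled mean by about 0.022 from the first-portion mean. The margin over 0.20 needed for significance is about 1.05 × 0.41/√43 = 0.066. This is a reason to show results by portion, not an error in the test.

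In sum: a free improvement with a small expected effect.

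**What to change.** - In SAP 2.3.1 and 2.3.2, state that the trend regressions, when run on the pooled data, include study portion (OPTALYSE PE or UK extension) as a fixed factor.
- In Appendix 1 item 17, name the model for the pooled 6-minute walk between-group comparison and include the same factor.
- In pooled Tables 11, 12 and 15, give arm counts by portion and add an OPTALYSE PE column beside the UK-alone and pooled estimates.
- Leave the one-sample t tests against 0.20 and the per-arm MMRM as they are on this point.

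The cost is one degree of freedom per model and some table columns. In the assumed 14/9/6 UK split the standard error goes from 0.0441 to 0.0445. No new data are needed.

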2.3 Efficacy Analyses

2.3.1 Primary Efficacy Analysis

The primary efficacy outcome is the change in the RV diameter-to-LV diameter ratio, from Screening/Baseline to 48 ± 6 hours after the start of the APT procedure, as determined by CTA. For each treatment arm, the mean RV/LV ratio change will be compared to the historical control value of a 0.20 reduction for the heparin arm¹. For this study, a 1-sided $p < 0.15$ by t test rejecting a ≤ 0.20 reduction will be regarded as a positive sign for further investigating a treatment regimen. As an example, should the standard deviation be 0.41 as observed in the SEATTLE II study, with 25 evaluable subjects the 1-sided p value would be <0.15 if the mean RV/LV ratio reduction is 0.29 or higher. To limit the 3-arm total false positive error rate to 0.15, the Hochberg procedure² will be used for statistical testing.

The main primary endpoint analyses will be performed for the ITT Subject Set and the Evaluable Subjects subset.

To explore a potential increasing trend in RV/LV ratio reduction for treatment Groups 1 through 3 as defined in Protocol Synopsis, i.e. Group 1 having the least reduction and Group 3 having the most reduction, an exploratory regression analysis will be performed on both absolute change and percent change data from all 3 groups. The independent variables will include baseline RV/LV ratio value, the unilateral vs. bilateral PE indicator, and treatment groups 1 through 3 coded ordinally as 1, 2, and 3. This exploratory analysis will only be performed on the ITT Subject Set.

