10.5 Sample Size And Power Estimation

The primary efficacy endpoint for the study is the 48-hour decrease in RV/LV ratio. The Fasullo study's heparin arm indicated a mean RV/LV ratio decrease of 0.20. Based on these results, we propose a mean 48-hour RV/LV ratio (absolute) decrease ≤ 0.20 as the null hypothesis for this study. Rejecting the null hypothesis with a 1-sided $p<0.15$ by t test will be regarded as a positive sign for further investigating a treatment regimen. For sub-massive PE subjects in the SEATTLE II study, a mean RV/LV ratio reduction of 0.43 was observed with a standard deviation of 0.41. Should these results be true for a regimen in the current study, with 25 evaluable subjects, the power to detect a positive signal is approximately 0.95.

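### The plan does not say whether an arm's positive sign means raw one-sided p<0.15 or Hochberg rejection, and its 0.29 threshold and 0.96/0.95 per-regimen power are unadjusted figures

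*SAP*

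**What the plan says.** SAP 2.3.1 compares each arm's mean RV/LV change with a historical reduction of 0.20. A one-sided t-test p<0.15 against that null "will be regarded as a positive sign for further investigating a treatment regimen". The example follows: at SD 0.41, "with 25 evaluable subjects the 1-sided p value would be <0.15 if the mean RV/LV ratio reduction is 0.29 or higher". The paragraph closes by naming the multiplicity method: "To limit the 3-arm total false positive error rate to 0.15, the Hochberg procedure" is to be used for the testing. Protocol 10.3.1 has the same sequence.

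SAP 2.5 sets "48-hour RV/LV ratio (absolute) decrease ≤ 0.20 as the null hypothesis for this study", repeats the p<0.15 criterion without adjustment and, for a true reduction of 0.43, says that "with 25 evaluable subjects, the power to detect a positive signal is approximately 0.96". Protocol 10.5 makes the same calculation and says "the power to detect a positive signal is approximately 0.95". SAP 2.5 alone adds a simultaneous Hochberg power of about 0.88 for the three groups.

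SAP Appendix 1, item 11, which specifies the primary table, asks for one- and two-sided t-test p values. It lists no Hochberg-adjusted p value or Hochberg decision.

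**The concern.** Two criteria are given for one decision, and no sentence ranks them. Under Hochberg, p<0.15 is enough for an arm only if the other two arms also reach 0.15. Otherwise the arm needs p at or below 0.075 together with a second such arm, or p at or below 0.05 on its own. An arm with a raw p between 0.05 and 0.15 can therefore be positive by one sentence and not rejected by the next.

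The trial's objective is to find the best of three regimens, so mixed results across arms are a case of real interest, and that is where the rules part. If the raw rule is followed, the stated 0.15 error rate is not held. If Hochberg is followed, the stated threshold and per-regimen power hold only when the other arms pass as well. If the choice is left open, it could be made after the results are seen.

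**Working it through.** **Inputs.** Null reduction 0.20, assumed true reduction 0.43, SD 0.41, 25 evaluable per arm (SAP 2.5, Protocol 10.5). One-sided level 0.15, three arms, Hochberg (SAP 2.3.1, Protocol 10.3.1). I assume independent arms, normally distributed changes and a common SD.

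**1. The plan's own figures.**
- Standard error = 0.41/√25 = 0.082. The critical t on 24 df at one-sided 0.15 is 1.059.
- Threshold = 0.20 + 1.059 × 0.082 = 0.287. The p value is 0.142 at a mean of 0.29 and 0.169 at 0.28, so the stated 0.29 is right to two decimals.
- Noncentrality = (0.43 − 0.20)/0.082 = 2.805. Power at 0.15 is 0.9588, which agrees with 0.96 and, as an approximation, with 0.95.
- Hochberg rejects in all three arms exactly when the largest p is at most 0.15. Simultaneous power is therefore 0.9588³ = 0.881, the stated 0.88.

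Every stated figure reproduces. The 0.29 and the 0.96/0.95 come from the unadjusted 0.15 level.

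**2. Error rate of the raw rule.** With all three arms at the null, 1 − 0.85³ = 0.386. Under Hochberg, simulation (1,000,000 trials) gives 0.145.

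**3. Hochberg steps at n=25, SD 0.41.**

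| Step level | Critical t | Minimum mean reduction | Chance of p ≤ level at true 0.43 |
|---|---|---|---|
| 0.15 (all three arms pass) | 1.059 | 0.287 | 0.9588 |
| 0.075 (a second arm also passes) | 1.487 | 0.322 | 0.9038 |
| 0.05 (alone) | 1.711 | 0.340 | 0.8598 |

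**4. Hochberg power for one regimen at 0.43.** The arm is rejected in three situations:
- p ≤ 0.05, whatever the other arms do;
- p between 0.05 and 0.075, if at least one other arm is ≤ 0.075 or both others are ≤ 0.15 (probability A);
- p between 0.075 and 0.15, if both others are ≤ 0.15 (probability B).

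The interval probabilities are 0.9038 − 0.8598 = 0.0440 and 0.9588 − 0.9038 = 0.0550, so power = 0.8598 + 0.0440 × A + 0.0550 × B.

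- All three arms at 0.43: A = 1 − 0.0962² + 0.0550² = 0.9938; B = 0.9588² = 0.9193; power = 0.8598 + 0.0437 + 0.0506 = 0.954.
- One other arm at 0.43, the third at 0.20: A = 1 − 0.0962 × 0.925 + 0.0550 × 0.075 = 0.9151; B = 0.9588 × 0.15 = 0.1438; power = 0.8598 + 0.0403 + 0.0079 = 0.908.
- Both others at 0.20: A = 1 − 0.925² + 0.075² = 0.150; B = 0.15² = 0.0225; power = 0.8598 + 0.0066 + 0.0012 = 0.868.

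Simulation gave 0.954, 0.908 and 0.867. If the other arms cannot pass at all, the floor is 0.86.

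**5. How often the rules disagree for that regimen.** This is raw power minus Hochberg power: 0.9588 − 0.954 = 0.005, 0.9588 − 0.908 = 0.051, and 0.9588 − 0.868 = 0.091. With all arms at the null, the rules differ on at least one arm in 26% of simulated trials.

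**The case against.** The strongest reply is that the paragraph describes one procedure in sequence: a per-arm test and its level, an example, then the method that governs testing across arms. On that reading 0.15 is the error level, Hochberg is how it is spent, and 0.386 belongs to a rule the plan never adopts. This is a fair reading, and SAP 2.5 supports it by quoting a Hochberg power. A reader might infer that the plan contains two contradictory rules. The documents do not support that: the Hochberg sentence can be taken as the control placed on the p<0.15 criterion, and the two coincide when all three arms pass. What remains is that the term positive sign is attached only to the raw p value and never tied to Hochberg rejection.

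A reader might also infer that 0.29 and 0.96 are miscalculated or have nothing to do with Hochberg. Neither is so. The 0.29 sentence is offered as an example, speaks only of when the raw p falls below 0.15, and is true. It is also Hochberg's threshold when all three arms pass. With all three arms at 0.43, Hochberg power is 0.954, close to 0.96 and equal to the Protocol's rounded 0.95. The SAP's 0.88 is a correct Hochberg figure.

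Nor does item 11 prevent Hochberg from being applied: it supplies the three one-sided p values that the procedure needs. It only omits the result. Finally, the practical gap is small if every regimen works as assumed, about 0.5% of trials for a given arm. It reaches 5% to 9% when one or two arms do not work.

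**Conclusion.** The point stands as an unresolved decision rule, not as a calculation error. Read as written for each arm, the raw criterion does not deliver the 0.15 three-arm error rate that the same paragraph promises: it gives 0.386. Read with Hochberg, the stated threshold holds only when all three arms pass and rises to 0.32 or 0.34 otherwise. Per-regimen power at a true reduction of 0.43 runs from 0.95 with three effective arms through 0.91 with two to 0.87 with one, where an ineffective arm has a true reduction of 0.20.

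The 0.88 is the chance of rejecting in all three arms when all three are effective. A reader might take it as the chance of detecting a single effective regimen under Hochberg, and it is not that.

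Severity is moderate, because the outcome only screens a regimen for further study. The figures rest on independent arms, normal data, SD 0.41 and the planned 25 evaluable per arm. They do not describe the UK extension as it ended: the SAP synopsis reports 29 subjects enrolled in total. The smaller sample changes the power but does not settle which rule applies.

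**What to change.** - In SAP 2.3.1 and Protocol 10.3.1, add one clause: a positive sign means rejection of the 0.20 null under the Hochberg procedure at one-sided 0.15.
- Keep the 0.29 example and the 0.96 (SAP 2.5) and 0.95 (Protocol 10.5), labelled as unadjusted. Beside them give the Hochberg thresholds of 0.32 at the 0.075 step and 0.34 at the 0.05 step, and the Hochberg per-regimen power range of 0.87 to 0.95 with the number of effective arms that each value assumes.
- In SAP 2.5, label 0.88 as the power to reject in all three arms when all three are effective.
- In SAP Appendix 1, item 11, add the Hochberg-adjusted p value or the Hochberg decision beside the raw p values.
- Say that these design figures refer to 25 evaluable per arm.

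The cost is a clause, some labels and one table column, with no new data and no design change. The stated per-regimen power becomes somewhat less favourable when not every arm works.
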